2.1 Primary objective

Evaluate the proportion of patients in the Pre- and Post-discharge treatment initiation groups achieving the target dose of 200 mg LCZ696 bid at the end of the week-10 after randomization (Treatment Epoch), regardless of previous temporary dose interruption or down-titration.

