Patients randomized to treatment initiation **Post**-discharge will continue to be treated with optimized standard of care HF-medications (i.e., locally commercially available ACEI or ARB, beta-blockers, and other HF-guidelines therapy at the discretion of the treating physician). They could receive the first LCZ696 dose at any point between the **day after discharge** and **up to 14 days after Discharge** (i.e., Discharge occurred on 01-Oct-2016: Post-discharge treatment may start at any time *between the day after Discharge and 15-Oct-2016*), implementing the required mandatory 36 hours wash-out if a patient is on current ACEI therapy.

Prolonged hospital stay

Duration of hospitalization in the various countries may vary broadly. Across the globe, the average length of hospital stay is about 5–10 days (Ponikowski P, 2014). However, some patients may prolong their hospital stay for reasons other than worsening of HF conditions,

and the investigator must document the details for the prolongation in the source documentation. To allow for the variability and unplanned lengthening of hospital stay, provisions are made to enable initiation of the LCZ696 therapy, as indicated below.

1. If assigned to **Pre-**discharge treatment, patients *will continue* LCZ696 treatment as per investigator's directions.

The date for the Discharge visit (Visit 102) assessments will be calculated as the date of Randomization + 1 week (i.e., Randomization on 07-Mar-2016; Visit 102 will be on 14-Mar-2016). All assessment will be completed and entered in the CRF page for Visit 102

Visit 103 (2 weeks after-Randomization) will be calculated as the date of Randomization + 2 weeks (i.e., Randomization on 07-Mar-2016; Visit 103 will be on 21-Mar-2016). All subsequent visit dates will be derived from the date of Visit 103 (i.e., visit 104 = Visit 103 + 2 weeks).

2. If assigned to **Post**-discharge AND in the hospital on day 10 AFTER Randomization: All the **assessments indicated for the Discharge visit** (Visit 102) should be carried out **at least 2 days before** starting LCZ696 treatment. All the results will be reported in the Discharge page of the CRFs. Also, the mandatory 36 h washout for ACEI must be completed.

Patients may start LCZ696 treatment, as early as 12 days but no later than 21 days after the RANDOMIZATION date, while remaining in the hospital.

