The date when such patient starts LCZ696 treatment will represents Visit 103 and all assessment related to that visit must also be completed. All subsequent visit dates will be derived from the date of Visit 103 (i.e., visit 104 = Visit 103 + 2 weeks).

If a patient is Randomized but not treated with LCZ696 within the windows provided:

- For the **Pre-discharge** group within 7 days after Randomization;
- For the Post-discharge group either
 - a. within 2 weeks after discharge
- b. or, if due to prolonged hospital stay, between 12 and 21 days after Randomization the patient should be withdrawn.

For more details on study treatment, please refer to Section 5, and refer to the Assessment Schedule for the visit frequency during the study.

To identify early in the course of the study any potential safety or tolerability issues, two interim safety analyses will be carried out by an internal independent DMC when 30% and 60% of the patients have completed the visit at 10-weeks after Randomization (Visit 199) to assess if the study should be terminated early.

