5.5.9 Discontinuation of study treatment

During the **Treatment Epoch** (up to 10 weeks after Randomization), *permanent* discontinuation of LCZ696 treatment should NOT be considered withdrawn from the study. The patient should return for the assessments indicated for Visit 199 (10-weeks after Randomization), if discontinued before that visit, and Visit 199 will be also the End of Study visit for that patient. If they fail to return for these assessments for unknown reasons, every effort (*e.g.* telephone, e-mail, letter) should be made to contact them as specified in Section 5.5.11.

During the **Follow-up Epoch**, *permanent* discontinuation of LCZ696 constitutes withdrawal from the study. Under these circumstances, the patient should be evaluated at a final study visit but will not undergo assessments thereafter unless additional follow-up is required due to prior occurrence of an adverse event.

The investigator must also notify the IRT of the patient's *permanent* discontinuation of LCZ696 and record it on the Drug Administration Record of the eCRFs.

The emergence of the following circumstances will require LCZ696 discontinuation:

- Withdrawal of informed consent
- Failure to follow study-related instructions
- Pregnancy (Section 7.7)
- Use of prohibited treatment
- Investigator thinks that continuation would be detrimental to the patient's well-being

LCZ696 may be permanently discontinued at the investigator's discretion if any of the following occurs:

- Any severe suspected drug-related AE
- Suspected occurrence of angioedema. A patient with any signs or symptoms of clinically significant angioedema should be thoroughly evaluated by the investigator and constitute a reason for discontinuation of study medication.

Depending on the serum potassium, blood pressure, or eGFR, patients may need to have their LCZ696 dose or the dose of another concomitant medication reduced or discontinued, or, if appropriate, have potentially contributing agents adjusted. Please refer to Appendices 3, 4, and 5 for treatment guidelines for hyperkalemia, hypotension, or renal dysfunction, respectively.

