Specific circumstances surrounding missed or rescheduled visits must be discussed with the study monitor. Missed or rescheduled visits SHOULD NOT LEAD automatically to patient discontinuation.

For patients who permanently discontinue LCZ696 during the Treatment Epoch (up to visit 199), irrespective of the treatment assignment group, the last date of LCZ696 administration will be entered in the drug administration records (DAR) page of the CRFs. However, the patient will be followed-up and should return to the site for all remaining visits up to Visit 199 (10 weeks after Randomization) but will not return for the Follow-up epoch.

Enrolled patients withdrawing from the study for any reasons during the Follow-up Epoch should be scheduled for a visit as soon as possible, at which time all of the assessments listed

for End of Study visit (EoS, Visit 299) will be performed. At this final visit all dispensed medication supplies should be reconciled and the Adverse Events and Concomitant Medications updated on their respective CRFs.

Page 40

Documentation of attempts to contact the patient who do not report for the EoS visit, and are lost to follow-up, should be recorded in the source documentation.

Table 6-1 Assessment table

Epoch	Screen- ing				Treatm	ent						F	Follow-เ	ір
Visit	1	101 Random -ization	Start date of Pre -discharge treatment	102 Discharge	Start date of Post- discharge	103	104	105	106	199 & TD and/or PPW	201	202	203	End of Study Visit 299 & TD and/or PPW
Day	-3-to-1	1				14§	28§							
Weeks AFTER Randomization						2§	4 §	6§	8§	10§	14 ^Φ	18 ^Ф	22 ^ф	26 ^ф
Weeks of follow-up											4	8	12	16
Obtain informed consent	Х													
Entry criteria review	Х													
Demography	X													
Medical History	Х													
Alcohol and smoking history	Х													
ECG	S	Х		Х						Х				Х
Signs & Symptoms	S	Х		X						Х				X
NYHA class		X		Х						Х				Х
Prior & Concomitant HF Medications	X Å	X		X _Φ		X	XΔ	XΔ	XΔ	XΔ	XΔ	XΔ	XΔ	X _Φ
Physical Exam	S													S
Height	Х													

Epoch	Screen- ing				Treatm	nent						F	Follow-เ	ір
Visit	1	101 Random -ization	Start date of Pre -discharge treatment	102 Discharge	Start date of Post- discharge	103	104	105	106	199 & TD and/or PPW	201	202	203	End of Study Visit 299 & TD and/or PPW
Day	-3-to-1	1				14§	28§							
Weeks AFTER Randomization						2§	4 §	6§	8 §	10§	14 ^Φ	18 ^Ф	22 [¢]	26 ^ф
Weeks of follow-up											4	8	12	16
Weight	S	Х		S						S				S
Vital signs	Х	Χ□		Х		Χ	Х	Χ	Χ	Х	Χ	Х	Х	X

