A sample size of approximately 1000 randomized patients (about 930 patients for ARB and ACEI, and about 70 in the naïve group) provides reasonable precision across a range of possible outcomes.

Stratification will occur prior to Randomization and it will be based on the patient's HF therapy prior to admission (i.e., ACEI, ARBs, or 'ACEI/ARB-inhibition-naïve treatment'). Stratification will ensure that within a stratum the distribution between Pre- and Post-discharge is similar. It is expected that the naïve patients will represent at least 7% of the total number of patients (i.e., 70 patients from in total 1000 randomized patients). For the samples size of 1000 patients, a maximum of 930 of ACEI or ARB-treated patients will be randomized, to ensure achieving the minimum target of 70 ACEI/ARB-naïve patients. However, more than 70 RAAS inhibition-naïve treatment patients could be included if during the study conduct a higher number is enrolled. Stratification will be performed at the country level.

Randomization/treatment assignment will be accomplished through the Interactive Response Technology (IRT).

The primary analysis time point is Week 10 after randomization. In the primary analysis, no imputation will be used for any patients who discontinue study therapy due to adverse events or abnormal laboratory values prematurely.

Two interim analyses of tolerability and safety will be carried out during the study when 30% and 60% of the patients have completed the visit at 10-weeks after Randomization (Visit 199). Details will be pre-specified in the Charter of the DMC.

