Three periods will be considered for the AEs analysis:

- 10 weeks of treatment epoch which is defined as the initial 10 weeks after randomization: all AEs started during the 10 weeks of treatment epoch will be included;
- 16-weeks follow-up epoch which is defined as the additional 16 weeks after the treatment epoch: all AEs started during the follow-up epoch will be included;
- 26 weeks duration which is defined as the whole study from the randomization date up to the end of study date.

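### Does the re-based visit calendar for long-stay Post-discharge patients leave the week-10 endpoints without a usable reference date?

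*Protocol*

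**What the plan says.** Under the prolonged-stay provisions of Protocol Section 3.1, a Post-discharge patient still in hospital on day 10 may start LCZ696 there "as early as 12 days but no later than 21 days after the RANDOMIZATION date". For that patient, "The date when such patient starts LCZ696 treatment will represents Visit 103", and every later visit is counted from it at two-week steps. A long-stay Pre-discharge patient keeps the ordinary calendar: "Visit 103 (2 weeks after-Randomization) will be calculated as the date of Randomization + 2 weeks".

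The primary endpoint (Protocol Section 9.4.1, SAP Section 2.5.1) and the secondary endpoint descriptions (Protocol Section 6.5.2, SAP Section 1.2.5) give 10 weeks after randomization with Visit 199 in brackets, as if the two always coincided.

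Elsewhere the calendar date dominates:
- The primary objective (Protocol Section 2.1) is "achieving the target dose of 200 mg LCZ696 bid at the end of the week-10 after randomization (Treatment Epoch").
- SAP Section 1.1 states: "The primary analysis time point is Week 10 after randomization".
- Protocol Section 5.5.9 describes the Treatment Epoch as "up to 10 weeks after Randomization".
- SAP Section 2.8.1 has "10 weeks of treatment epoch which is defined as the initial 10 weeks after randomization".
- Protocol Section 9.5.2 and SAP Section 2.8, which define the secondary variables for analysis, refer to week 10 after randomization and never mention Visit 199.

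The one text pulling the other way is in Protocol Section 6, on patients who "permanently discontinue LCZ696 during the Treatment Epoch (up to visit 199").

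**The concern.** For these patients Visit 199 need not fall at 10 weeks. The re-basing applies to one arm only, in a trial where investigators know the arm and decide each titration step. If the endpoint is read at Visit 199, a patient who starts on days 15 to 21 gains one to seven days in which to reach target or to discontinue, and a patient who starts on day 12 or 13 loses two days or one.

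A related gap affects both arms. Table 6-1 allows a dose change at Visit 199, and the published SAP does not say whether 200 mg first dispensed there is a success. At stake are the primary endpoint, the two endpoints that require a dose held for two weeks, and discontinuation for adverse events by week 10.

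**Working it through.** Days are counted from the randomization date as day 0. Under the SAP Section 2.1.1 convention, day 70 is Study Day 71.

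**Reproducing the plan.** Visit 199 = Visit 103 + 4 × 14 days. With Visit 103 on day 14, Visit 199 = 14 + 56 = day 70, the 10 weeks of Table 6-1. For the precision statement, take 80% in both arms and 500 per arm: SE of log RR = √[2 × 0.20/(0.80 × 500)] = √0.001 = 0.0316, and exp(±1.96 × 0.0316) = 0.94 to 1.06, as stated.

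**Long-stay Post-discharge, first dose on day d.** Visit 106 = d + 42 and Visit 199 = d + 56. A dose begun at Visit 106 has been held 14 days at Visit 199, and 70 − (d + 42) = 28 − d days at day 70.

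| d | Visit 106 | Visit 199 | Offset from day 70 | Days held at day 70 |
|---|---|---|---|---|
| 12 | 54 | 68 | −2 | 16 |
| 14 | 56 | 70 | 0 | 14 |
| 15 | 57 | 71 | +1 | 13 |
| 17 | 59 | 73 | +3 | 11 |
| 18 | 60 | 74 | +4 | 10 |
| 21 | 63 | 77 | +7 | 7 |

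Every patient in both arms has a window of ±3 days, so an ordinary Visit 199 may fall on day 67 to 73. Starts on days 12 to 17 stay within that range. Only starts on days 18 to 21 are scheduled beyond it.

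**Where the two dates can disagree.**
1. Primary: no scheduled visit lies between day 70 and a later Visit 199. The readings part only through an unscheduled change or through 200 mg first dispensed at Visit 199.
2. Two-week endpoints: a dose restarted or raised at Visit 106 passes at Visit 199 but falls short at day 70 for starts on days 15 to 21. The definitions in SAP Section 2.8 settle this by the calendar date.
3. Discontinuation: a stop between day 70 and a later Visit 199. SAP Section 2.8 again bounds it at week 10. The adverse-event periods in Section 2.8.1 sort events by start date, so a different boundary there is no contradiction.

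**Size, primary endpoint.** With k Post-discharge patients reclassified as failures, RR = 0.80/(0.80 − k/500).
- k = 1: 0.80/0.798 = 1.0025, a change of 0.2 percentage points.
- k = 5: 0.80/0.79 = 1.013.
- k = 10: 0.80/0.78 = 1.026.
- k = 23 (4.6% of the arm): 0.80/0.754 = 1.061, about the half-width of the planned interval.

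The long-stay share is not given. Protocol Section 3.1 puts the average total stay at about 5 to 10 days, and this group is still in hospital 10 days after randomization, so it is probably small. Assumed range: 5 to 50 of 500 patients, 10% to 20% reclassified. The low end is 5 × 0.10 = 0.5 patient, RR 1.001. The high end is 50 × 0.20 = 10 patients, RR 1.026. Reaching k = 23 would take 23/50 = 46% of even the largest assumed group.

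**Size, discontinuation for adverse events.** Each patient counts for more on a rarer event. Taking the 5.9% run-in figure in Protocol Section 3.6 as an assumed rate in both arms, removing one Post-discharge event gives 5.9/5.7 = 1.035. The interval at that rate has SE = √[2 × 0.941/(0.059 × 500)] = 0.253, hence 0.61 to 1.64.

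**The case for a change.** The strongest argument for acting is that the re-basing rule is specific and covers all later visits, so the general instruction in Protocol Section 6 that a moved visit does not move the next one cannot be relied on to hold Visit 199 at day 70. The same-day gap also leans towards one arm. A 50 mg start doubled at four-week steps, which Section 5.5.4 permits, reaches 200 mg at first dose + 56 days, exactly Visit 199 for every long-stay Post-discharge patient. A Pre-discharge patient starts by day 7 and completes the same steps by day 7 + 56 = 63. One sentence written before database lock would cost almost nothing.

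The dates, the missing tie-break and the lean all stand. The claim that the plan is evenly divided does not. The phrase in Section 6 is an attendance instruction, and its own paragraph equates Visit 199 with 10 weeks. On the same-day dose, Protocol Section 9.4.3 and SAP Section 2.5.3 speak of achieving and maintaining the target. That is not a complete rule, but it weighs against a dose first handed out that day.

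Nor would a fixed day-70 rule be a clear gain. Under it, 200 mg first dispensed at an in-window Visit 199 on days 67 to 69 would count, and on days 71 to 73 would not. That brings visit timing into both arms to tidy a small subgroup.

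**Conclusion.** This is a gap that analysts can fill sensibly, and no change to the plan follows. Most of the text, including the analysis definitions of all three secondary variables, points to 10 weeks by the calendar. SAP Section 5.1.1 makes dosing start and end dates mandatory, so the dose on that day can be derived for patients with dosing records. An analyst who used Visit 199 instead would still reach a sound result: the risk ratio moves by at most about 0.026 under the assumptions above, against a half-width of about 0.06, and SAP Section 5.4.1 plans estimation with no test.

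This rests on the long-stay share and the reclassified fraction, both assumed, and on 80% success with 500 per arm, the plan's own illustration. Parts of the SAP are redacted and the data set specifications named in its Section 1 are not in the published text, so an explicit derivation may already exist there.

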Premature subject/patient withdrawal	Point/time when the patient exits from the study prior to the planned completion of all study treatment administration and/or assessments; at this time all study treatment administration is discontinued and no further assessments are planned, unless the patient will be followed for progression and/or survival
Randomization number	A unique identifier assigned to each randomized patient, corresponding to a specific treatment arm assignment
Study drug/ treatment	Any single drug or combination of drugs administered to the patient as part of the required study procedures; includes investigational drug (s), active drug run-ins or background therapy
Study/investigatio nal treatment discontinuation	Point/time when patient permanently stops taking study/investigational treatment for any reason; may or may not also be the point/time of premature patient withdrawal
Subject Number	A number assigned to each patient who enrolls into the study
Variable	A measured value or assessed response that is determined in specific assessments and used in data analysis to evaluate the drug being tested in the study

Amendment 2

Purpose of this amendment is to address the following changes:

- Section 3.1 (Study design) minor wording changes were entered to clarify:
 - o the duration of hemodynamic stabilization (i.e., no need for IV diuretics in the past 24 hours prior to signing ICF) with respect to the timing of ICF administration (first bullet under "ICF should be administered");
 - o a redundant statement on Randomization was deleted on page 18;
 - o for patients randomized to Pre-discharge group, with a prolonged hospital stay, details on the Discharge visit (Visit 102) assessments are edited on page 20 (bullet No. 1).
- Section 4.1 Inclusion criteria number 7: clarification for the 24-hour duration of hemodynamically stable conditions at Screening prior to signing ICF.
- Section 5.4: Editorial changes were made to clarify that the sponsor clinical team blinding status during the study will not be compromised.
- Section 6, Assessment table (Table 6-1) a missing check was added under Discharge, visit 102, to clarify that IRT should be notified of the visit date.
- Section 6.5.7.3: Clarifying text has been added on the parameters of local laboratory dipstick assessment to consistently reflect the CRF page.
- Section 6.5.8: Clarification on Screening ECG data have been added.

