9.4.3 Handling of missing values/censoring/discontinuations

In the primary analysis, no imputation will be used for any patients, who discontinue study therapy due to adverse events or abnormal laboratory values. All patients who prematurely discontinue, and do not achieve and maintain the target dose of LCZ696 200 mg bid at 10 weeks after randomization will be regarded as 10 week up-titration failures. Information of patients discontinuing study drug or participation in trial visits will be collected whenever possible and will be used in the analysis. In patients who could not be followed up for the primary endpoint, it is aimed to at least determine the vital status of the patients at the final visit. For the supplementary analysis, patients who prematurely discontinue due to administrative reasons (non-AE or non-death) will defined as non-evaluable, and thus be excluded from the analysis.

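### Randomised patients who miss the LCZ696 start window are withdrawn without scheduled follow-up to week 10, while patients who start and then stop are followed to Visit 199

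*Protocol*

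**What the plan says.** Protocol Section 3.1 sets the start windows. For Pre-discharge the limit is "within 7 days after Randomization". For Post-discharge it is "within 2 weeks after discharge" or, after a prolonged stay, "as early as 12 days but no later than 21 days after the RANDOMIZATION date". The list closes with "if due to prolonged hospital stay, between 12 and 21 days after Randomization the patient should be withdrawn". The final clause governs every item, so it applies to both arms.

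The glossary entry on premature withdrawal says that treatment stops and "no further assessments are planned, unless the patient will be followed for progression and/or survival".

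Section 5.5.9 treats patients who have started differently. During the Treatment Epoch, permanent "discontinuation of LCZ696 treatment should NOT be considered withdrawn from the study", and the patient returns for Visit 199. Section 6 goes further and asks for all remaining visits up to Visit 199.

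Three provisions could reach a never-started patient:

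- Table 6-1 heads the week-10 column as serving Visit 199 and also treatment discontinuation or premature patient withdrawal (PPW).
- Protocol Section 9.4.3, repeated in SAP Section 2.5.3, says that for patients who could not be followed for the primary endpoint "it is aimed to at least determine the vital status of the patients at the final visit". Both sections also promise to collect information on patients who stop attending visits where possible.
- Section 7.3.2 requires all-cause SAE reporting until 30 days after the last study visit. After that, only SAEs suspected to be related to study treatment are reported.

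**The concern.** Two patients randomised on the same day, one who takes a single dose and one who takes none, get different follow-up. Missing the window is not withdrawal of consent in the sense of Section 5.5.10, so the protocol itself ends the observation.

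The loss is unlikely to be random. Section 3.6 makes starting LCZ696 conditional on blood pressure and serum potassium, so patients who cannot start probably include the less stable ones. The windows also differ in length and setting between arms, so the number lost may differ by arm.

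Section 3.2 says the study should capture every hospitalisation over its duration. A comparison of deaths, hospitalisations or SAEs to week 10 in everyone randomised would be incomplete for this group. No later choice of analysis set can restore data that were not collected.

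**Working it through.** **The plan's own figure.** The documents give no never-start rate and no figure for follow-up loss. Their only design figure is the precision statement (Protocol Section 9.7, SAP Section 3). With 500 per arm and 80% success in both, SE of log RR = √(0.2/(500×0.8) + 0.2/(500×0.8)) = 0.0316. The interval is exp(±1.96×0.0316) = 0.94 to 1.06, as stated. The point here does not depend on it.

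**Inputs for the follow-up gap**, in days after randomisation:

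- Visit 199 is at week 10, day 70 (Table 6-1).
- The Pre-discharge window closes on day 7 (Section 3.1).
- The Post-discharge window closes 14 days after discharge, or on day 21 after a prolonged stay (Section 3.1).
- Discharge on day 2 to day 10 is assumed for the usual Post-discharge route. The protocol summary places randomisation at least 48 hours before planned discharge, and a patient still in hospital on day 10 takes the prolonged-stay route.
- SAE reporting runs 30 days beyond the last visit (Section 7.3.2).
- The last contact is assumed to be day W, the day the window closes.

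**Formulas.** Days without scheduled visits = 70 − W. Days without routine SAE reporting = 70 − (W + 30).

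| Route | W | 70 − W | SAE reporting ends (W + 30) | Days without SAE reporting |
|---|---|---|---|---|
| Pre-discharge | 7 | 63 | 37 | 33 |
| Post-discharge, discharged day 2 | 16 | 54 | 46 | 24 |
| Post-discharge, prolonged stay | 21 | 49 | 51 | 19 |
| Post-discharge, discharged day 10 | 24 | 46 | 54 | 16 |

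A closing visit held later than day W shortens each gap by the same number of days. Non-serious events after the last visit are not captured at all.

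**Which arm loses more.** Each never-started patient loses more time in the Pre-discharge arm. On the usual route, the Post-discharge arm loses more in total only if its never-start rate exceeds the Pre-discharge rate by these factors:

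- visits: 63/54 = 1.2 to 63/46 = 1.4;
- SAE reporting: 33/24 = 1.4 to 33/16 = 2.1.

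The prolonged-stay route lies within both ranges (63/49 = 1.3 and 33/19 = 1.7). The documents do not say whether these factors are reached.

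**Would the current analyses use the data?** Largely not:

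- The SAF requires at least one dose.
- The SAP's FAS excludes patients not starting within the window (deviation OTH13).
- The AE analysis since randomisation (SAP Section 2.8.1) ends at the last dose, so it defines no interval for a patient who never had one.
- RAN is the only set that keeps these patients.

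**The case against.** The strongest reply is that the documents do not abandon these patients. The glossary entry has an exception for survival follow-up. Table 6-1 provides a PPW visit. Section 9.4.3 and SAP Section 2.5.3 aim for vital status and for whatever information can be had. All-cause SAEs, which include deaths and most hospitalisations, are reported for a further 30 days. A reader might infer that no assessment takes place after withdrawal and that week-10 vital status goes uncollected. The documents do not support that.

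These provisions narrow the gap but do not close it:

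- The text spells out a withdrawal visit only for the Follow-up Epoch. A PPW visit at the time of withdrawal would not be a week-10 observation.
- The vital-status provision is an aim, and its final visit may be the withdrawal visit.
- No survival follow-up is specified for this group, so the glossary exception has nothing to act on.
- SAE reporting depends on the site learning of the event, with no contact scheduled to prompt it. After 30 days it requires suspected relation to a drug the patient never took.

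The second reply is that the stated objectives hardly suffer, and that stands. The primary endpoint and the dose-attainment secondary endpoints concern the LCZ696 dose taken, which is known for a patient who never started. Such patients are outside the SAF in any case, which is a separate matter of analysis-set definition. Safety has no formal inference. Some SAP objective text is redacted, so any planned hospitalisation analysis cannot be judged.

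**Conclusion.** The difference in follow-up is real and conflicts with the aim in Section 3.2. If the last contact is the day the window closes, each never-started patient lacks routine SAE capture for about 33 days (Pre-discharge) or 16 to 24 days (Post-discharge) before week 10, and scheduled visits for 63 or 46 to 54 days. The Post-discharge figures also assume discharge between day 2 and day 10 on the usual route.

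The change is worth making for the completeness of all-randomised safety data. It is not a threat to the primary result.

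Three stronger inferences should be resisted:

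- *That the loss is worse in the Post-discharge arm.* The longer, partly outpatient window makes this plausible. But no rate by arm is given, the gap per patient is longer in the Pre-discharge arm, and that arm must fit any ACEI washout and a first dose in before discharge.
- *That the number of patients can be estimated from the 24% rehospitalisation at 12 weeks in Section 3.2.* That rate counts from discharge. It does not apply to the in-hospital Pre-discharge window or to the Post-discharge days before discharge, and nothing in the documents gives the share of rehospitalised patients who would miss the window.
- *That follow-up is already covered by consent.* The consent pages are not in the public documents, so this cannot be checked.

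**What to change.** In Protocol Section 3.1, replace the closing withdrawal instruction with a statement that the patient is recorded as not having started LCZ696 within the window. The patient stays in the study and attends Visit 199 or, at minimum, has a week-10 contact for vital status, hospitalisations and SAEs, unless consent is withdrawn. State that SAE reporting for these patients runs at least to that contact.

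In the SAP, add a summary of deaths, hospitalisations and SAEs from randomisation to week 10, by randomised arm in the RAN population. Show the number never started and the number without week-10 information in each arm. Without this addition, the current SAF and FAS analyses would leave the extra data unused.

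Reconcile Section 3.1 with the SAP's OTH13 rule. Section 3.1 withdraws patients not treated within the window, whereas the SAP keeps those dosed outside it in the SAF and so in the primary analysis.

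Treatment rules and sample size do not change. The cost is one visit or telephone contact per never-started patient. The number is presumably small, though the documents give no rate. The consent form should be checked to confirm that it covers the contact.
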